8 STATISTICAL ANALYSIS

8.1 General Considerations

The analysis will be performed for each part, and presented by treatment group, unless specified otherwise. The treatment groups are defined as follows:

- Part 1: *F508del*/MF genotype group
 - VX-152 100mg q12h + VX-661/IVA, VX-152 200mg q12h + VX-661/IVA, VX-152 300mg q12h + VX-661/IVA, and placebo, with VX-661 component administered as 100 mg qd and IVA component administered as 150 mg q12h.
- Part 2: *F508del/F508del* genotype group
 - VX-152 200mg q12h + VX-661/IVA, VX-152 300mg q12h + VX-661/IVA, VX-661/IVA, VX-661/IVA, VX-661/IVA from Cohort 2A and VX-661/IVA from Cohort 2B, with VX-661 component administered as 100 mg qd and IVA component administered as 150 mg q12h.

The Schedule of Assessments is provided in Appendix A. The precision standards for reporting safety and efficacy variables are provided in an internal Biometrics document that specifies the programming rules including the precision for derived variables.

All individual subject data for those randomized or dosed with any amount of study drug will be presented in data listings.

Continuous variables will be summarized using the following descriptive summary statistics: the number of subjects (n), mean, SD, standard error (SE), median, minimum value (min), and maximum value (max). SE may not be reported for safety summary tables.

Categorical variables will be summarized using counts and percentages. Percentages will be presented to 1 decimal place.

Baseline value, unless otherwise specified, will be defined as the most recent non-missing measurement (scheduled or unscheduled) collected before the first dose of study drug on Day 1 of the Treatment Period. For ECG, baseline will be defined as the most recent non-missing measurement (or the average of triplicate measurements, if the most recent non-missing measurement is obtained in triplicate), before the first dose of study drug on Day 1 of the Treatment Period.

Absolute change from baseline will be calculated as postbaseline value – baseline value.

Relative change from baseline will be calculated as (postbaseline value – baseline value)/baseline value.

Treatment-emergent (TE) period for Part 1 will include the time from the first dose of study drug in the Treatment Period to the Safety Follow-up (SFU) Visit, or 28 Days after the last dose of study drug for subjects who do not complete the SFU Visit.

For Part 2, the TE period will be defined separately for the Run-In Period, and the Treatment Period:

- The TE period for the Run-in Period will include the time from the first dose of study drug in the Run-in Period to: (1) the last day prior to the first dose of study drug in the Treatment Period for subjects who complete the Run-in Period and continue to the Treatment Period, or (2) the SFU Visit for subjects who did not continue to the Treatment Period and have an SFU Visit, or (3) 28 days after the last dose of study drug in the Run-in Period for subjects who do not have an SFU Visit (e.g., subjects who do not meet the criteria to enter the Treatment Period and re-enter Study 661-110). Only data collected up to the end of study for a subject will be included in analysis.
- The TE period for the Treatment Period will include the first dose of study drug in the Treatment Period to: (1) the SFU Visit, or (2) 28 days after the last dose of study drug for subjects who do not have an SFU Visit (e.g. subjects whose Early Treatment Termination (ETT) Visit occurs 3 weeks or later following the last dose of study drug and the ETT visit replaces the SFU visit, or who leave the study early and re-enter Study 661-110). Only data collected up to the end of study for a subject will be included in analysis.

Unscheduled visits: Unscheduled visit measurements will be included in analysis as follows:

- In scheduled visit windows per specified visit windowing rules.
- In the derivation of baseline/last on-treatment measurements.
- In the derivation of maximum/minimum on-treatment values and maximum/minimum change from baseline values for safety analyses.
- In individual subject data listings as appropriate.

Visit windowing rules: The analysis visit windows for protocol-defined visits are provided in Appendix B.

Spirometry ($ppFEV_1$) will be used for both efficacy and safety purposes. For efficacy analysis, the assessments will follow the visit windowing rules for efficacy. For safety analysis, the assessments at 5 hours post-dose on nominal days 1 and 15 will be used.

Incomplete/missing data will not be imputed, unless specified otherwise.

Outliers: No formal statistical analyses will be performed to detect or remedy the presence of statistical outliers, unless specified otherwise.

Multiplicity: There will be no multiplicity adjustment for performing multiple hypothesis tests, unless specified otherwise.

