- ^e All screening results must be reviewed before the subject receives VX-661/IVA in the Run-in Period on Day -28, unless noted otherwise.
- ^f The Day -14 Visit is only required for subjects who are naïve to VX-661/IVA treatment.
- ^g Days 3, 5, and 11 assessments may be collected at the clinic, at a local laboratory, or during a visit by a qualified individual (e.g., home nurse).
- ^h Day 3 and Day 5 assessments will be performed at least 2 days apart, with the first day of assessments occurring no earlier than Day 3 and the second day of assessments occurring no later than Day 6. (i.e., Assessments will be performed on Days 3 and 5, Days 4 and 6, or Days 3 and 6.)
- ⁱ Randomization may occur on the previous day (Day -1) after all inclusion and exclusion criteria and criteria for entry into the Treatment Period have been confirmed. See [Section 8.1.3](#).
- ^j CFQ-R must be completed before the start of any other assessments scheduled at that visit.
- ^k The predose assessment on Day 1 may be performed on the previous day (Day -1) if randomization has occurred.
- ^l Subjects will complete the CFQ-R at the ETT Visit only if it has been 2 weeks or more since their last visit.

Table 3-2 Study VX16-152-102: Schedule of Assessments for Part 2, Cohort 2A

Event/Assessment ^a	Screening	Run-in Period		Treatment Period ^b					Washout Period	ETT Visit ^c	Safety Follow-up 28 (± 7) Days After Last Dose ^d
	Days -56 to -29 ^e	Day -28 (± 1 day)	Day -14 ^f (± 1 day)	Day 1	Days 3 and 5 ^g (or Days 4/6 or Days 3/6) ^h	Day 8 (± 1 day)	Day 11 ^g (± 1 day)	Day 15 (± 1 day)	Day 29 (± 3 days)		
Height ^m	X										
Vital signs ⁿ	X	X		X		X		X	X	X	X
Pulse oximetry ⁿ	X	X		X		X		X	X	X	X
Physical examination ^o	Complete	Abbreviated		Abbreviated		Abbreviated		Abbreviated	Abbreviated	Abbreviated	Complete
Ophthalmologic examination ^p	X										
Standard 12-lead ECG ^q	X	X		X		X		X	X	X	X
Sweat chloride ^{k,r}	X		X	X		X		X	X	X	
Spirometry ^s	X		X	X		X		X	X	X	X
Urinalysis ^k	X	X		X		X		X	X	X	X

^m Weight and height will be measured with shoes off.

ⁿ Vital signs and pulse oximetry will be collected after the subject has been seated for at least 5 minutes.

^o Complete and abbreviated PEs are described in [Section 11.7.3](#). Symptom-targeted PEs will occur at any time during the study if triggered by AEs or if deemed necessary by the investigator or healthcare provider.

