^p The ophthalmological examination can be performed at any time during the Screening Period through the Day 1 Visit (before the first dose of study drug). The screening ophthalmological examination does not have to be performed if there is documentation of an examination that met protocol criteria and was within 3 months before the date of informed consent, or if there is documentation of bilateral lens removal for the subject.

^q All standard 12-lead ECGs will be performed after the subject has been seated for at least 5 minutes. ECGs will be collected before procedures that may affect heart rate (e.g., blood sampling). On Days 1 and 15, ECGs will be collected before dosing and 4 hours (± 1 hour) after dosing. At all other visits, ECGs will be collected before dosing (as applicable). ECGs collected on Day 1 before dosing will be performed in triplicate.

^r Sweat chloride will be measured in all subjects. If the value cannot be determined from the screening test, a sweat chloride value documented in the subject's medical record may be used to establish eligibility.

^s Spirometry may be performed pre- or post-bronchodilator at the Screening Visit. Spirometry will be performed pre-bronchodilator, before the morning dose of study drugs, and should be performed at approximately the same time at every other study visit. On Days 1 and 15, spirometry will also be performed pre-bronchodilator 5 hours (± 1 hour) after study drug administration.

Table 3-2 Study VX16-152-102: Schedule of Assessments for Part 2, Cohort 2A

Event/Assessment ^a	Screening	Run-in Period		Treatment Period ^b					Washout Period	ETT Visit ^c	Safety Follow-up 28 (± 7) Days After Last Dose ^d
	Days -56 to -29 ^e	Day -28 (± 1 day)	Day -14 ^f (± 1 day)	Day 1	Days 3 and 5 ^g (or Days 4/6 or Days 3/6) ^h	Day 8 (± 1 day)	Day 11 ^g (± 1 day)	Day 15 (± 1 day)	Day 29 (± 3 days)		
Pregnancy test (all females of childbearing potential)	Serum	Urine		Urine				Urine		Serum	Serum
CFTR genotype ^t	X										
FSH ^u	X										
G6PD activity test ^v	X										
Serum chemistry and hematology ^k	X	X		X	X ^{g,x}	X	X ^{g,x}	X	X	X	X
Coagulation ^k	X	X		X		X		X			X
PK sampling ^y				X		X		X		X ^y	
VX-661/IVA dosing ^z		Day -28 through Day 29									

^t *CFTR* genotyping will be performed for all subjects. If the screening *CFTR* genotype result is not received before Day -28, a previous *CFTR* genotype laboratory report may be used to establish eligibility.

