8.1.2 Run-in Period (Part 2)

The Run-in Period will have a total duration of 4 weeks and is designed to establish a reliable on-treatment (VX-661/IVA) baseline for the Treatment Period. The first dose of VX-661/IVA will be administered at the Day -28 Visit. The last dose of VX-661/IVA within the Run-in Period will be administered in the evening of Day -1 (1 day before the Day 1 Visit).

Study eligibility for Part 2 subjects will be confirmed before the first dose of VX-661/IVA in the Run-in Period (on Day -28).

Study visits during the Run-in Period will occur as shown in [Table 3-2](#) and [Table 3-3](#). All visits will occur within the windows specified.

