9.3 Prohibited Medications

Medications that are prohibited in this study (Screening Period through the Safety Follow-up Visit) are shown in Table 9-1. VX-152, VX-661, and IVA are metabolized extensively via cytochrome P450 (CYP) 3A4. VX-152 is also metabolized by CYP2C9. Therefore, the use of moderate and strong inducers of CYP3A or CYP2C9 and strong and moderate inhibitors of CYP3A, which have the potential to alter the exposure of VX-152, VX-661, or IVA, will be restricted in this study. VX-152 was shown in vitro to be an inhibitor of the hepatic transporters organic anion transporting polypeptide 1B1 (OATP1B1) and 1B3 (OATP1B3). Therefore, sensitive substrates of OATP1B1/1B3, such as HMG Co-A Reductase Inhibitors (i.e., “statins”), are also restricted during the study.

A non-exhaustive list of study prohibitions and cautions for medication will be provided in the Study Reference Manual.

Table 9-1 Study Restrictions

Medication	Timing of Restriction	
	Start of Restriction	End of Restriction
Moderate and strong CYP3A or CYP2C9 inducers	None allowed within 14 days before the first dose of the study drug on Day 1 (Part 1) or Day -28 (Part 2)	None allowed through the Safety Follow-up Visit
Moderate and strong CYP3A inhibitors (except ciprofloxacin)	None allowed within 14 days before the first dose of the study drug on Day 1 (Part 1) or Day -28 (Part 2)	None allowed through the Safety Follow-up Visit
Sensitive OATP1B1/1B3 substrates	None allowed within 14 days before the first dose of VX-152 or placebo on Day 1	None allowed until after last dose of VX-152 or placebo
Commercially available CFTR modulators (e.g., Kalydeco, Orkambi)	Part 1: None allowed within 14 days before screening Part 2: None allowed from the start of the Run-in Period	Part 1: None allowed through the Safety Follow-up Visit Part 2: None allowed through the end of the Washout Period

Note: The use of restricted medication by subjects with medical needs will be addressed on a case-by-case basis with the medical monitor.

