12.3.1 General Considerations

Continuous variables will be summarized using the following descriptive summary statistics: the number of subjects (n), mean, SD, standard error (SE), median, minimum value (min), and maximum value (max). The precision of the measurement for each continuous variable will be specified in the SAP. Unless otherwise specified, minimum and maximum values will be reported with the same precision as the units of the raw data. The mean, median, SD, and SE will be reported to 1 additional decimal place. Any values that require a transformation to standard units (metric or International System [SI]) will be converted with the appropriate precision.

Categorical variables will be summarized using counts and percentages. Percentages will be presented to 1 decimal place.

The **baseline** value, unless otherwise specified, will be defined as the most recent non-missing measurement (scheduled or unscheduled) collected before the first dose of study drug in the Treatment Period (i.e., Day 1). For ECG, baseline will be defined as the average of the most recent triplicate pretreatment measurements before the first dose of study drug in the Treatment Period (i.e., Day 1).

Absolute change from baseline will be calculated as postbaseline value – baseline value.

Relative change from baseline will be calculated as (postbaseline value – baseline value)/baseline value.

The Treatment-emergent (TE) Period will include the time from the first dose in the Treatment Period to the Safety Follow-up Visit or 28 days after the last dose of the study drug for subjects who do not complete the Safety Follow-up Visit. Additional TE periods related to the Run-in period will be defined in the SAP, as appropriate.

There will be no multiplicity adjustment for performing multiple hypothesis tests.

The rules for handling missing data due to treatment or study discontinuation will be described in the SAP.

All data will be summarized for Parts 1 and 2, separately, unless specified otherwise.

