8.4 Pharmacodynamic Analysis

The sweat chloride measurement for a given visit will be calculated as the mean of the nonmissing sweat chloride measurements obtained on the left and right arms at that visit. If one of the two arm measurements at a time point is missing, the other will be used as the mean. A volume $\geq 15 \ \mu$ L is required for an accurate determination of sweat chloride. Any results reported as having volume <15 μ L will be considered missing. Any sweat chloride values reported as <10 mmol/L or >160 mmol/L will be considered missing.

The analysis of the pharmacodynamic (PD) effect of VX-152 in TC with VX-661/IVA (all parts) on sweat chloride concentrations will be described in this section.

8.4.1.1 Primary Analysis of the Dose Response trend of absolute change in sweat chloride from baseline at Day 15 in Part 1

The null hypothesis to be tested is that the dose response of the mean absolute change from baseline at Day 15 for sweat chloride is not decreasing between placebo and the TC dose groups. The test will be performed using the MCP procedure with the pre-specified contrasts provided in Section 6.2.2.1, within a linear MMRM framework using PROC GLIMMIX in SAS. The model will include treatment group, visit, and treatment-by-visit interaction as fixed effects, with continuous baseline sweat chloride as a covariate. The dose response test will be based on the 1-sided maximum *t*-statistic of the individual *t*-statistics for the multiple pre-specified contrasts at alpha = 5%, based on the treatment group means at Day 15, using a compound symmetry covariance structure for the within-subject errors

The presentation of results for the treatment effect at Day 15, and the treatment effect by visit will be similar to the primary analysis of the primary efficacy variable. The corresponding P value for the decreasing dose response trend will be provided. In addition, descriptive analyses of the change from baseline will be performed for all treatment groups at each postbaseline visit. A waterfall plot showing the subject-level absolute change from baseline in sweat chloride at Day 15 will be presented, by treatment group.

[figure not shown]
8.4.1.2 Absolute change in sweat chloride from baseline at Day 15 (Part 2 Cohort 2A) and through Day 29 (Part 2 Cohort 2B)

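### The Part 2 baseline rule does not require an on-VX-661/IVA value for sweat chloride or ppFEV1, so a few subjects could be measured from an off-drug screening value

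*SAP*

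**What the plan says.** SAP 8.1 takes as baseline the "most recent non-missing measurement (scheduled or unscheduled) collected before the first dose of study drug on Day 1 of the Treatment Period". Protocol 12.3.1 has the same rule: "most recent non-missing measurement (scheduled or unscheduled) collected before the first dose of study drug in the Treatment Period". Both apply unless otherwise specified. In SAP Appendix B the baseline window for sweat chloride and spirometry is study day 1 or earlier, with no lower limit.

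Protocol 8.1.2 says the run-in "is designed to establish a reliable on-treatment (VX-661/IVA) baseline for the Treatment Period".

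Before Day 1, Protocol Tables 3-2 and 3-3 schedule sweat chloride and spirometry only at Screening (Days -56 to -29) and Day -14. The footnote on Day -14 limits it: "The Day -14 Visit is only required for subjects who are" naive to VX-661/IVA. Exclusion criterion 14 admits subjects with ongoing or prior participation in a VX-661/IVA study, and Part 2 needs no washout before Day -28. For commercial CFTR modulators, the Part 2 restriction in Table 9-1 reads "None allowed from the start of the Run-in Period".

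Two further rules bear on this. SAP 8.4 treats low-volume sweat samples as missing, and adds: "Any sweat chloride values reported as <10 mmol/L or >160 mmol/L will be considered missing". The schedule footnote on spirometry says "Spirometry may be performed pre- or post-bronchodilator at the Screening Visit", whereas later visits are to be pre-bronchodilator.

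**The concern.** In Part 2 the change from baseline is meant to isolate VX-152 added to established VX-661/IVA. That requires a baseline on VX-661/IVA, and nothing in the rule secures it. The SAP separates the Run-in Period from the Treatment Period for treatment-emergent periods, medications and adverse events, but not for baseline.

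If an off-drug screening value is used, the subject's change contains the VX-661/IVA run-in effect as well as any VX-152 effect. The hypothesis in SAP 8.3.1.1 is within-group and 1-sided (mean ppFEV1 change not greater than zero on triple combination), and SAP 8.4.1.2 analyses Part 2 sweat chloride in the same way. Randomization does not protect a within-group test from a baseline taken in the wrong state.

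Spirometry has a second mismatch, in both Parts: the screening value may be post-bronchodilator and the follow-up pre-bronchodilator. Protocol 11.6.1 itself wants matched states, since a subject who is post-bronchodilator on Day 1 stays so afterwards.

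**Working it through.** **1. Which value the rule returns when Day 1 is unusable (Part 2, sweat chloride and ppFEV1)**

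- *Naive to VX-661/IVA:* Day -14, two weeks into VX-661/IVA. Protocol 8.2.2 reports that in earlier studies most of the effect was present by 14 days, so this is essentially the intended state. Only if Day -14 is missing too does the rule reach Screening, off VX-661/IVA (possibly on a commercial modulator, which is barred only from the start of the run-in).
- *Entering from Study 661-110 without interruption:* Screening, which may be done while still in that study. Normally on VX-661/IVA, so no problem of drug state.
- *Past but not current VX-661/IVA use:* not naive on a plain reading, so no Day -14 visit is required. One unusable Day 1 value leads straight to an off-drug screening value. On rescreening, sweat chloride is not repeated (Protocol 8.1.1.2), so that value may be older still.

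CFQ-R has no scheduled Part 2 assessment before Day 1 and is not affected.

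**2. The plan's own inputs**

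The SDs are 13 mmol/L and 8 percentage points; the groups are 9:3 (Cohort 2A) and 18:6 (Cohort 2B). Power = P(T > t(0.95, n-1)), with T noncentral t on n-1 degrees of freedom and noncentrality (mean/SD)·√n. This reproduces SAP Tables 6-4 and 6-5:

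- Sweat chloride (10, 15, 20 mmol/L): n=9, 67.8%, 93.4%, 99.5%; n=18, 93.1%, 99.9%, >99.9%.
- ppFEV1 (3, 5, 7 points): n=9, 27.0%, 52.8%, 77.3%; n=18, 45.3%, 81.6%, 97.2%.

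No stated figure is in dispute.

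**3. Shift from one affected subject**

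Let D be the difference between off-drug and on-VX-661/IVA values. The documents do not give it; 5 to 10 mmol/L and 3 to 4 ppFEV1 points are assumptions. Before covariate adjustment the group mean shifts by D/n; SE = SD/√n.

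| n | Sweat chloride shift (mmol/L) | SE | Shift/SE | ppFEV1 shift (points) | SE | Shift/SE |
|---|---|---|---|---|---|---|
| 9 | 0.56–1.11 | 4.33 | 0.13–0.26 | 0.33–0.44 | 2.67 | 0.13–0.17 |
| 18 | 0.28–0.56 | 3.06 | 0.09–0.18 | 0.17–0.22 | 1.89 | 0.09–0.12 |
| 3 (comparator) | 1.67–3.33 | 7.51 | 0.22–0.44 | 1.00–1.33 | 4.62 | 0.22–0.29 |
| 6 (comparator) | 0.83–1.67 | 5.31 | 0.16–0.31 | 0.50–0.67 | 3.27 | 0.15–0.20 |

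**4. Effect on the 1-sided 5% within-group test**

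Simulated t-test, no covariate, 200,000 runs per case, with wider assumed D of 5 to 15 mmol/L and 2 to 6 points:

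- One of 9 affected: error 6.3–8.1% (sweat chloride), 5.7–7.3% (ppFEV1).
- One of 18: 5.8–7.5% and 5.7–6.7%.
- Two of 9: 7.7–13.1% and 6.5–10.3%.

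**5. What the baseline covariate does**

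Hold the baseline slope b fixed, between -1 and 0, and let N be the cohort total. One affected triple-combination subject shifts the adjusted within-group mean by D/n - |b|·D·(1/n - 1/N). With n/N = 9/12 or 18/24, the reduction is at most a quarter of D/n. The between-group difference shifts by (1 - |b|)·D/n. The covariate therefore helps the between-group estimate more than the within-group test.

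**The case against.** A reader might infer that any missing Day 1 value in Part 2 is replaced by a Day -28 or screening value, and that the VX-661/IVA effect is routinely credited to VX-152. The documents do not support that. Sweat chloride and spirometry are not scheduled at Day -28. Naive subjects fall back first to an on-drug Day -14 value, and uninterrupted Study 661-110 subjects are normally on drug at screening. Sweat is collected from both arms and either one suffices (Protocol 11.4.1, SAP 8.4), so both must fail. Day 1 predose sweat may be taken on Day -1, and unscheduled run-in values count. The routes that remain need a coincidence, or past exposure to a drug still in Phase 3, and the documents do not define naive.

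A second tempting inference is bias in favor of VX-152 against the comparator. The same rule applies to both randomized arms before any Treatment Period dose, so the difference is not biased in expectation. An affected comparator subject works against VX-152, and a post-bronchodilator baseline understates the gain.

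A third is that safety baselines need the same restriction. Chemistry, hematology, vital signs and ECG do have a pre-dose Day -28 value and no Day -14 value, so one unusable Day 1 result can give a pre-VX-661/IVA baseline. But safety analysis is descriptive, and a restriction would leave these measures with no scheduled fallback. Applied to every measurement, it would also remove baseline height and BMI, since height is measured only at Screening.

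All of this stands and limits the point. What it does not answer is that the rule as written can return an off-drug baseline for the endpoints that the run-in was designed to serve.

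**Conclusion.** The gap is real but narrow. The Part 2 rule does not secure an on-VX-661/IVA baseline for sweat chloride or ppFEV1, and in two foreseeable but uncommon situations it returns an off-drug screening value. The within-group tests are exposed. The between-group estimates gain noise, which counts most where the comparator has 3 or 6 subjects.

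With the assumed effects of 5 to 10 mmol/L or 3 to 4 points, one affected triple-combination subject moves the mean by at most 0.26 standard errors. At the upper end of the wider range, 15 mmol/L with n=9, it is 15/9 = 1.67 mmol/L, or 0.38 standard errors. The documents give neither the VX-661/IVA effect nor a rate of missing Day 1 values; 0 to 2 affected subjects is a judgment. For spirometry the bronchodilator mismatch acts in the opposite direction, so the net ppFEV1 shift for a given subject could have either sign. These are secondary objectives in a safety study, and the point disturbs neither the sample size nor the primary objective.

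**What to change.** Add to SAP 8.1, for sweat chloride and ppFEV1 only:

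- In Part 2, baseline is the latest non-missing value, scheduled or unscheduled, taken on VX-661/IVA at or after the Day -14 visit and before the first Treatment Period dose.
- A screening value qualifies only for a subject on uninterrupted VX-661/IVA from Study 661-110. Otherwise baseline is missing for that endpoint.
- In both Parts, a post-bronchodilator screening spirometry value is not used as baseline for pre-bronchodilator follow-up.

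Put the same lower limit in the Cohort 2A and 2B sweat chloride and spirometry baseline windows of Appendix B. Leave the rule unchanged for height, weight, BMI and safety measures, but flag in the listings any Part 2 safety baseline taken before the first run-in dose.

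The cost is a few sentences and no new data. Because the protocol rule applies unless otherwise specified, the SAP can carry the change. It should be settled before the first unblinded model-based interim analysis, since choosing baselines for individual subjects afterwards would be post hoc. The downside is that an occasional subject drops out of that endpoint's model, in line with the SAP default of no imputation. In a comparator group of 3 that is a third of the arm, so the number excluded for this reason should be reported by arm.
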